### 6.6. HARMS AND SAFETY

See [Table 5.1](#). The safety of each device will be summarized in the interim and final report. Overall summary of adverse events will be presented for each device. Total frequencies and percentages of adverse events for each Wright device will be summarized for the following factors:

- Procedure-Related Adverse Event / Incident
- Device-Related Adverse Event / Incident
- Device Failure
- Unanticipated Adverse Device Event
- Serious Adverse Event (SAE)
- Hospitalization SAE Outcome
- Treatment Required for the AE

The occurrence and rate of SAE will be further categorized by the outcome of the SAE (i.e., death, hospitalization).

The rates for device failure will be the basis of the survival rates for each device. The above AE factors will also be summarized for each study site.

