## **7.0 Statistical Considerations**

### **7.1 Study design**

This study is a global, multi-center, post-market observational study to demonstrate the safety and performance of the Wright products listed in Section 3.3. Data will be collected at baseline, surgery, at the last scheduled standard of care and/or surgeon release follow-up (FU) time point. The subjects improvement in post-surgical quality of life will be assessed using EQ-5D-5L and Foot and Ankle Ability Measure (FAAM).

An adverse event resulting from the presence or performance of the device and removal due to implant failure will determine the survivorship of the Wright product. Further, safety will be assessed by subject experience of device complication and adverse events during the study period.

All effectiveness and safety analysis will be performed separately for each Wright Medical device included in the study.

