### **7.3 Data Analysis**

Improvements in subject quality of life after surgery will be assessed by constructing 95% confidence interval for the mean change from baseline score in EQ-5D-5L and FAMM total and component scores.

|   |  |  |
|---|--|--|
|  | Clinical Investigation Plan
Foot and Ankle Products | CIP- INT19-MDR-001
Version: 2 |
|---|--|--|

Survivorship of a Wright product will be assessed based on adverse event resulting from the presence or performance of the device. The Kaplan Meier survivorship method and life table analysis will be employed. Time to adverse event due to the presence or performance of the implant will be the survivorship endpoint for each Wright device. Also, time to reoperation to exchange or remove any part of the Wright device due to failure of the implant will also determine the Wright product survivorship. Subjects who will not experience these events will be censored at the last follow-up visit. The Kaplan Meier survival curve and the 95% Confidence Interval will be constructed.

Safety endpoints will include all adverse events (AE), serious AE (SAE), unanticipated adverse device effects (UADEs).

All subjects enrolled in the study will be assessed for safety. Adverse events and other safety evaluations will be reported as frequency and rates as appropriate, cumulative over the different follow-up schedules.

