## 8.2. Appendix 2 – Listing of Tables and Listings, Table Templates

### A. LISTING OF TABLES

Table	1.1	Subject Accounting
Table	1.2	Subject Eligibility
Table	1.3	Demographics and Clinical Characteristics
Table	1.4	All Protocol Deviations
Table	1.5	Medical History
Table	2.1	Surgical and Operative Information
Table	2.2	Additional Surgical Procedures Performed
Table	3.1	EQ-5D by device and visit
Table	3.2.1	FAAM score by device and visit
Table	3.2.2	FAAM overall rating by Device and Visit
Table	4.1	Surgeon assessment by device
Table	4.2	Radiographic assessment by device
Table	5.1	Life table for time to first device related adverse event by device
Table	5.2	Life table for device failure by device
Table	5.3	Life table for time to death by device
Table	6.1	Adverse event by device

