**Table 5.1 Adverse Events by device.**

Adverse Events	Device 1		...		Device k	
	Subjects (%)	Events	Subjects (%)	Events	Subjects (%)	Events
Procedure-Related	xx (xx.x%)	xx			xx (xx.x%)	xx
Device-Related	xx (xx.x%)	xx			xx (xx.x%)	xx
Device Failure	xx (xx.x%)	xx			xx (xx.x%)	xx
Unanticipated AE	xx (xx.x%)	xx			xx (xx.x%)	xx
Serious AE	xx (xx.x%)	xx			xx (xx.x%)	xx
Hospitalization	xx (xx.x%)	xx			xx (xx.x%)	xx
Death	xx (xx.x%)	xx			xx (xx.x%)	xx
Required Treatment	xx (xx.x%)	xx			xx (xx.x%)	xx
Physical Therapy	xx (xx.x%)	xx			xx (xx.x%)	xx
Medication	xx (xx.x%)	xx			xx (xx.x%)	xx
Surgery	xx (xx.x%)	xx			xx (xx.x%)	xx
Other	xx (xx.x%)	xx			xx (xx.x%)	xx

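### The SAP promises an overall adverse event summary per device, but neither its list of factors nor its table shell has an any-AE line

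*SAP*

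**What the plan says.** Protocol 7.3 sets the safety endpoints: "Safety endpoints will include all adverse events (AE), serious AE (SAE), unanticipated adverse device effects (UADEs". On reporting it says "Adverse events and other safety evaluations will be reported as frequency and rates as appropriate", cumulative over the follow-up schedules. Protocol 11.1.1 defines an AE regardless of whether it is thought related to the intervention. Protocol 7.1 fixes the unit of analysis: "All effectiveness and safety analysis will be performed separately for each Wright Medical device included in the study".

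SAP 6.6 opens its safety plan with "Overall summary of adverse events will be presented for each device" and continues: "Total frequencies and percentages of adverse events for each Wright device will be summarized for the following factors". Seven factors follow: procedure-related, device-related, device failure, unanticipated adverse device event, serious AE, hospitalization as an SAE outcome, and treatment required. The same list serves the site breakdown: "The above AE factors will also be summarized for each study site".

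The shell in SAP Appendix 2B is headed "Table 5.1 Adverse Events by device". Appendix 2A lists the table as 6.1, "adverse event by device", and gives the number 5.1 to a life table. The point does not depend on the numbering; I give both so that the table can be found.

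SAP 3.1 limits summary tables to devices implanted in at least 10 patients and sends the rest to listings. SAP 6 says that the templates are there to steer programming and reporting.

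**The concern.** The protocol names all AEs alongside SAEs and unanticipated device effects, so it treats them as an item in their own right. The SAP's opening sentence in 6.6 appears to honour that, but the detail beneath it consists only of subsets. The list and the shell agree with each other, so the missing line is not explained by an abbreviated mock-up. A programmer who followed both would produce a per-device table without the broadest of the endpoints in Protocol 7.3.

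What is at stake is how the table reads. The reader would see rates for overlapping categories, most of which depend on someone's judgement of relatedness, expectedness or seriousness, and no rate that is free of those judgements. One stated purpose of the study (Protocol 2.0, SAP 2.1) is to find side-effects not known before, and for that purpose an unattributed count is useful beside the attributed ones.

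**Working it through.** The plan gives no figure to reproduce here. The check is a count, followed by the question whether the missing line can be derived from what is shown.

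**1. Count the SAP 6.6 factors.** Procedure-related, device-related, device failure, unanticipated, serious, hospitalization, treatment required: 7. Any-AE factors: 0.

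**2. Count the shell rows.** Procedure-Related, Device-Related, Device Failure, Unanticipated AE, Serious AE, Hospitalization, Death, Required Treatment, Physical Therapy, Medication, Surgery, Other: 12. That is the 7 factors plus death plus four treatment types (7 + 1 + 4 = 12). The row *Other* follows the three named treatments, so it is a type of treatment and not a residual class of AE. Any-AE rows: 0.

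**3. Can the rows be added?** No, because they overlap. A device failure that is device-related, serious, hospitalized and treated by surgery fills Device-Related, Device Failure, Serious AE, Hospitalization, Required Treatment and Surgery: 6 rows for one event in one subject. A column total would count that subject six times.

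**4. Do the rows cover every AE?** No. The AE form records device relation and procedure relation as separate items (Protocol 11.3), so an event can be neither. If it is also expected, non-serious, untreated and not a device failure, it enters 0 rows. Death and hospitalization are seriousness criteria in Protocol 11.1.2, so a non-serious event does not reach those rows either.

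**5. What do the rows tell us about the any-AE rate?** For a device with N subjects, only that

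max(row count)/N ≤ any-AE proportion ≤ N/N = 100%.

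The upper limit carries no information. The lower limit is attained only if every subject with an AE appears in the largest row.

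**6. Size per subject.** At the SAP 3.1 threshold, N = 10, one subject whose AEs all fall outside the rows changes the any-AE percentage by 1/10 = 10 percentage points. For larger N the step is 1/N, so 10 points is the largest step for any device that is tabulated.

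**7. Where else would such an event appear?**
- Listing 9, at patient level, with no rate.
- Table 1.1, if the event led to discontinuation.
- The surgeon-observed AE (yes/no) item that SAP 6.5 places under Table 4.2, if the surgeon saw it. This item is not restricted by relatedness, seriousness or treatment. It is a final-visit assessment and has no row in the Table 4.2 shell. It does not accumulate intraoperative events (Protocol 6.3.5.2) or events found later through the yearly patient survey (Protocol 11.4.1).

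None of the three gives a cumulative percentage of subjects with any AE.

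**The case against.** The best reply is that the first sentence of SAP 6.6 stands alone as a commitment, and that the factor list breaks the summary down without exhausting it. SAP 3.1.2 also promises AE frequencies and rates in general terms, and the protocol still governs. On that reading this is a gap in drafting. I accept that: a reader might infer that the SAP has abandoned the all-AE endpoint, and the documents do not support so strong a claim. What remains is that the specific text and the shell, which are what gets programmed, do not contain the line.

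Second, the protocol says rates *as appropriate* and never names the percentage of subjects with any AE. This is also true. But a subject count with a percentage is the form the shell uses for every other AE category, so it is the natural form for this one.

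Third, SAP 3.1 says qualitative variables will be shown with row and column totals and missing proportions. If device relation were tabulated at all its levels, including missing, its total would be the number of AE events. The shell prints only the positive level, however, and the result would be events and not subjects.

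Fourth, the surgeon's yes/no item is a partial substitute, and a meaningful one given that 38 of the 43 devices in SAP Appendix 1 have only one-year follow-up. It covers part of the gap, for the reasons and within the limits given above.

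Fifth, the events that escape the table are those least informative about the device. Serious, device-related and procedure-related events, device failures and deaths all have rows. The analysis is descriptive, no hypothesis is tested, there are no stopping rules, and enrollment has ended. This stands, and it is why the point is minor.

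**Conclusion.** The point holds as a cheap improvement of minor severity. Followed as written, the AE table would deliver neither the all-AE endpoint of Protocol 7.3 nor the overall summary that SAP 6.6 promises, and the rows shown cannot be combined to supply it.

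The size is up to 10 percentage points per affected subject at the 10-patient threshold. The number of affected subjects is not in the documents and may be zero. A reader might infer that the reported AE rates will be biased downward or that AE data will be lost. Neither follows: each row would be correct for what it counts, the events are collected, and Listing 9 allows the rate to be worked out at any time.

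The conclusion assumes that the table is programmed from the 6.6 list and the shell, as SAP 6 indicates, and that no any-AE line is added at the programming stage.

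**What to change.** Add *Any AE* (subjects n/N, %, number of events) as the first factor in SAP 6.6 and as the first row of the adverse-events-by-device table, and carry it into the per-site summary. The list goes from 7 to 8 factors and the shell from 12 to 13 rows.

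The cost is one factor and one row, computed from data already on the AE form. No sample size or other design figure changes. The drawback is a higher headline rate that takes in events incidental to the device, so the row should be read beside the device-related and procedure-related rows, and a footnote can say so.

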**6.2.5 Expected duration of each subject's participation**

Based on varied definitions of product clinical lifetime, the follow-up period will be 12 weeks to 10 years

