### 2.2. CLINICAL INVESTIGATION DESIGN

This investigation is a global, multi-center, post-market observational study. The study planned to enroll 40 patients per device according to sample size calculations based on the EQ-5D (See study protocol). The enrollment period is expected to be 5 years. Based on the varied definitions of clinical lifetime for each device, the follow-up (FU) period will range 12 weeks to 10 years.

Data will be collected at baseline, surgery, at last scheduled standard of care and/or surgeon release FU time point. Additionally, PROMs and safety may be followed yearly to sufficiently assess the safety of the product over the clinical lifetime as needed based on the current risk analysis for the product.

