### 4.2. STATISTICAL INTERIM ANALYSES AND STOPPING GUIDANCE

Interim analyses will be performed on an annual basis. The progress of the clinical investigation will be reported together with the interim results on the variable level according to the analysis plan.

There will be no stopping rules specified for this clinical investigation.

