### 5. Population and Progress

All analysis will include all subjects implanted with any of the Wright devices listed in Appendix 1, hence called Treated population.

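### Serious adverse events, hospitalisation, unanticipated events and required treatment are reported only as crude percentages, with no allowance for unequal follow-up

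*SAP*

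**What the plan says.** SAP 6.6 sets the safety summary: "Total frequencies and percentages of adverse events for each Wright device will be summarized for the following factors". The factors include serious adverse events (SAEs), hospitalisation, unanticipated device events and treatment required. The shell, titled "Adverse Events by device", has two columns per device, subjects (%) and events. Surgery is a row under required treatment. There is no person-time, time window, number at risk or confidence interval. (SAP 6.6 and the shell call this Table 5.1. The list in Appendix 2A calls it Table 6.1 and gives 5.1 to a life table.)

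The shell does not name its denominator. The only population defined is in SAP 5: "All analysis will include all subjects implanted with any of the Wright devices listed in Appendix 1, hence called Treated population".

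On follow-up, SAP 2.2 says "the follow-up (FU) period will range 12 weeks to 10 years". The schedule in SAP 4.4 lets the final clinical visit fall anywhere between the operation and 1 year, and Protocol 6.3.4 leaves the timing to the physician. Later contact is a yearly set of questionnaires sent by the site (Protocol 6.3.5.3). SAP Appendix 1 lists 43 devices: 38 with 1 year of follow-up, four with 2 years and one with 10 years. SAP 4.2 adds "Interim analyses will be performed on an annual basis", and SAP 6.6 puts device safety in the interim as well as the final report.

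Protocol 7.3 asks for a time dimension: "Adverse events and other safety evaluations will be reported as frequency and rates as appropriate, cumulative over the different follow-up schedules". Appendix 2A lists life tables for time to first device-related event, device failure and death, and for nothing else.

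**The concern.** A subject last assessed at 12 weeks counts in the denominator exactly like one assessed at 1 year. If no event was recorded, that subject counts as event-free for the whole period. The crude percentage is therefore an average of risks over whatever follow-up each subject had, and describes no stated time point.

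This has two consequences. Within a device, the percentage falls below the risk at the planned horizon when some subjects are not ascertained to it. Across devices, a device planned for 10 years accumulates events over a longer period than one planned for 1 year, so equal hazards give unequal percentages. The longer-followed device can then exceed its own 1-year risk while still understating its 10-year risk.

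The life tables handle this for three outcomes. SAEs, hospitalisation, unanticipated events and required treatment have only the crude figure. The device-failure life table partly covers surgery to exchange or remove a failed device, but not other surgery. SAP 3.1 gives the performance and safety of each device as the study's goal, so these are figures that readers will use.

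**Working it through.** **What can be reproduced.** The plan gives no adverse event rate, non-return rate or distribution of observed follow-up, so there is no safety figure to check. Its one relevant calculation is the EQ-5D precision: (1.96 × 0.313 / 0.1)² = 37.6, so n = 38. It reproduces but does not bear on this point.

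**Assumptions for the illustration (not from the documents).** True 1-year risk R = 10%. A fraction f of subjects is ascertained only to 12 weeks and the rest to 1 year. Nothing is captured after the last contact, and stopping is unrelated to risk. Twelve weeks is the lower end of the stated follow-up range.

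**Formula.** Let L = −ln(1 − R) = 0.1054 and F(t) = 1 − exp(−L·t^k), with k = 1 for a constant hazard and k = 0.5 for an early-peaking Weibull hazard. The expected crude percentage is (1 − f)·R + f·F(12/52).

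- Constant hazard: F(12/52) = 1 − exp(−0.1054 × 0.2308) = 2.4%.
- Early-peaking hazard: F(12/52) = 1 − exp(−0.1054 × 0.4804) = 4.9%.

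| Fraction ascertained only to 12 weeks | Constant hazard | Early-peaking hazard |
|---|---|---|
| 0% | 10.0% | 10.0% |
| 20% | 8.5% | 9.0% |
| 25% | 0.75 × 10 + 0.25 × 2.40 = 8.1% | 0.75 × 10 + 0.25 × 4.94 = 8.7% |
| 50% | 6.2% | 7.5% |

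At 25% the relative shortfall is 19% or 13%. Under a constant hazard it passes 10% when f exceeds 0.10 / (1 − 0.24) = 0.13. For true risks of 5% and 20% the ratios of crude to true are nearly the same.

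**Between devices.** If two devices have the same hazard and every subject completes follow-up, F(t) gives 10.0% at 1 year, against 19.0% (constant) or 13.8% (early-peaking) at 2 years and 65.1% or 28.3% at 10 years.

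**Which remedy works.** In a simulation with f = 50% and a constant hazard, the crude percentage was 6.2%. The Kaplan-Meier 1-year risk was 10.1%, and the person-time rate of 0.106 per year converts to 10.1%. The person-time rate fails when the hazard is not constant. With k = 0.5 and complete follow-up, first events per unit time are F(t) divided by the integral of 1 − F from 0 to t:

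- 1 year: 0.100 / 0.932 = 10.7 per 100 patient-years.
- 10 years: 0.283 / 8.03 = 3.5 per 100 patient-years.

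The hazard is the same in both cases, yet the 10-year device looks about three times safer. Kaplan-Meier estimates at a fixed time do not have this problem.

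**The case against.** The case for leaving the table alone has real substance.

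- **Later events are not all lost.** A schedule footnote says surgical interventions and unscheduled visits are observed throughout participation. Protocol 11.4.1 requires an event form if a subject returns after the last scheduled follow-up, and SAE reporting within 24 hours of the site learning of the event. A reader might infer that nothing is recorded after the last visit, but the documents do not say so. Capture is incomplete, not absent, so for a given fraction, cut-off and hazard shape the figures above are near the upper end of the bias.
- **Twelve weeks is no listed device's planned follow-up.** Appendix 1 gives every device at least 1 year. A 12-week cut-off arises only if the 1-year questionnaire is not returned or the data are cut early, and no non-return rate is given.
- **Recent enrolment chiefly affects interim reports.** Enrolment was discontinued on 1 November 2021, but the final report comes at the end of the investigation (SAP 4.3) and Protocol 12.1 defines completion by the last subject's required visits. No data cut-off is stated, so short follow-up in the final table is an inference.
- **The plan is descriptive.** It has no hypothesis tests, analyses each device separately and plans no between-device comparison. Table 1.1 shows completers and losses by visit.
- **Sampling error dominates.** At the reporting threshold of 10 patients, a move from 10% to 8.1% is 0.19 of an event, and one event in 10 has an exact 95% interval of 0.3% to 44.5%.

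These points limit the size and importance of the problem without removing it. Table 1.1 shows attendance but does not adjust event rates. The statement in SAP 3.1 that rates use available data follows the sentence on device survival and sets no denominator for adverse events. Protocol 7.3 asks for cumulative rates over the follow-up schedules, and the shell cannot provide them.

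**Conclusion.** The point holds in a limited form. For SAEs, hospitalisation, unanticipated events and required treatment, the plan provides only a crude percentage with all implanted subjects as the implied denominator. It understates risk at a common horizon when some subjects are not ascertained to that horizon, and it should not be read across devices with different follow-up.

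The size is unknown. The range of 8.1% to 8.7% against a true 10% rests on an assumed risk, an assumed 25% ascertained only to 12 weeks, two assumed hazard shapes and no later capture. The bias is zero if everyone reaches the horizon and small for peri-operative events.

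A reader might go further and conclude that the reported safety rates are biased by a known amount, or that a planned device comparison is invalid. The documents support neither: they give no follow-up or event data and plan no such comparison. The life-table outcomes (first device-related event, device failure, death) are outside this point.

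**What to change.** In SAP 6.6 and the adverse event shell:

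1. Keep the crude counts and percentages, state the denominator, and label them as not adjusted for follow-up.
2. Show follow-up per device: median and range of time from surgery to the last contact at which adverse event status was obtained.
3. For time to first SAE, first hospitalisation and first adverse-event-related surgery, add Kaplan-Meier cumulative incidence (1 minus survival) at 1 year, and at later scheduled years where the device has them. Give the number at risk and a 95% confidence interval, and censor at that last contact. This extends the life-table method already planned and supplies the time dimension in Protocol 7.3.
4. Do not use events per 100 patient-years to compare devices with different follow-up lengths.

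The cost is a few table rows and one derived date. The data already planned suffice: operation date, event onset date and contact dates. Intervals will be wide for devices with about 10 patients, which correctly shows how little a low percentage proves there. The Kaplan-Meier estimate assumes that censoring is unrelated to risk. The SAP should say so, since removal of a subject's only study device ends participation (Protocol 6.2.2).
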